8.3. Exclusion Criteria

The participant may not enter the study if ANY of the following apply:

- 1. Age less than 18 years
- 2. Previous pneumonectomy on the infected side
- 3. Pleural collection not amenable to chest tube drainage
- 4. Has previously received intra-pleural fibrinolytics and /or DNase for this empyema (ipsilateral and deemed by the clinical team to be the same, ongoing infection)
- 5. Has a known sensitivity or allergy to DNase or tissue plasminogen activator
- 6. Participants who are pregnant or lactating
- 7. Patients with pleural infection and an estimated survival period of less than three months due to an unrelated pathological condition, such as metastatic lung carcinoma.
- 8. Participant who are unable to give informed consent (lacking capacity)

9. PROTOCOL PROCEDURES

The following table illustrates scheduled study related procedures and data collection

Procedure		Consent	Innetions	Follo	ow up visits		
	Screening	Baseline/ Randomisation	Inpatient Assessme	3 days¹	14 days	28 days	90 days
			nt(s)	+/- 2 days	+/- 3 days	+/- 3 days	+/- 3 days
Eligibility assessment	X	Х					
Informed consent	X ²	X ²					

Demographics R	х	Х					
Medical history ^R	Х	Х					
Clinical assessment R	Х	X	Х	X	Х	Х	Х
Concomitant medication ^R	X3	X ³					
Imaging routine – chest x ray R		Х			Х	Х	Х
Imaging routine – Thoracic Ultrasound ^R		Х	X (on days 3±1 and 5±1 post randomisatio n)	X	X	X	
Imaging routine – CT chest ^R	X ⁴	X ⁴	X ⁴				
Chest drain insertion or therapeutic aspiration in situ or planned	х	X					
Intrapleural enzyme therapy ^R			х				
Surgery ^R			Х				
Routine clinical bloods	Х	Х	х	Х	х	Х	
Routine pleural fluid ^R	Х						
Randomisation		X					
RAPID score		X ⁵					
Research pleural fluid collection and storage		Xe	X ₆				
Research blood collection and storage		X ⁶	X _e				
Breathlessness and/or pain (VAS) score		X ⁷			X ⁷	X ⁷	X ⁷

QOL: EQ-5D-5L	X ₈			X8	X8	X8
---------------	----------------	--	--	----	----	----

Assessment of functional ability (SF36)			X 9	X 9	X ⁹
Health utilization		Х			
Semi- structured interviews				X ¹⁰	

^R Indicates procedures or data collection that is part of routine care for all patients. The results of these are required to be collected and documented as part of the RAPTOR - f study, hence are included in this table.

¹ This will be applied to the low RAPID score group, please see the protocol for the details

² Informed consent will be taken within the first 24 hours after discussing the study and offering the participant information sheet.

³ If the participant had any antibiotics prior to admission to the hospital or if they are on anticoagulation or antiplatelet.

⁴ CT scan will be conducted as part of the usual care for all participants with pleural infection during the inpatient stay

⁵ The RAPID score will be calculated for the intervention group ONLY following randomisation.

⁶ The research samples (paired pleural fluid and blood) will be collected on day 1 (randomisation day) 0,3 and 5 post- randomisation (with the first week). This is optional, please see the protocol for the details of the process.

⁷ These assessments will take place in person at baseline, 14 days +/- 3, 28 days +/-3 days and remotely in 90 days +/- 3 days, please see protocol.

⁸ These will be collected at baseline, day 28 +/-3 days in person and day 90 +/- 3 days (remotely), please see protocol.

⁹ These assessments will take place at day 28 +_ 3 days and day 90+_ 3 days, please see protocol.

¹⁰The interview PIS will be given to the participant when attending the clinic in 2 weeks post-discharge and the interviews will take place between 4 to 6 weeks post-discharge, please see protocol

9.1. Recruitment

This feasibility study aims to recruit 30 patients from 3-4 UK centres (Oxford, Norfolk and Norwich, Plymouth and Royal Devon and Exeter with well-established pleural centres that will enroll eligible patients over 8-10 months. The sites are geographically distributed to ensure the population recruited is diverse and representative of the UK pleural infection population.

9.2. Screening and Eligibility Assessment

A member of the clinical team may identify participants with confirmed or suspected pleural infection. Due to the nature of the study, all participants will be in inpatient care at the time and will be offered the opportunity to participate at an early stage of their admission (by definition, within 24 hours of either confirmation of pleural infection or insertion of the chest tube for the treatment of pleural infection). The clinical team will approach potential participants and either the clinical or research team will then provide the participant with the participant information sheet and be available to answer any questions. Participants will be identified through respiratory and general wards or outpatient referrals, clinics, and ambulatory care.

There is no maximum time limit between screening and randomisation. However, due to the nature of the disease, treatment must not be delayed, so participants are likely to have less than 24 hours to consider enrolment following diagnosis of pleural infection with chest drain in situ or had therapeutic aspiration or both are planned.

Day 0 should be considered as the first contact with the research team and a decision on randomisation must be made by the end of day 1. If the participant remains eligible, randomisation is possible.

Pleural fluid samples required to confirm eligibility will be collected as part of clinical care and are not study-specific, therefore prior consent is not required. Research samples will be collected (paired blood and pleural samples) at day 1 (randomisation day), 3 and 5 post-randomisation following optional consent (agreement to collect pleural fluid 100 millilitres and blood 10 millilitres for research purposes). These samples will be transferred to the central site of the study for analysis of biomarkers.

Patients who are eligible for the RAPTOR f study but, following discussion and reading the study information sheet, decline enrolment into the study are defined as "screen failures". Despite no longer participating in the RAPTOR f feasibility study selected patients who decline entry may be invited to take part in semi-structured interviews to discuss their initial concepts and views of the study.

9.3. Informed Consent

Consent can be obtained **prior** to confirmation of pleural infection in participants who are likely to have a chest drain insertion or therapeutic pleural aspiration. These participants will be randomised once the eligibility criteria have been confirmed.

If pleural infection is ruled out, participants will not be required to continue in the study. The number of patients that have been screened in this manner will be recorded as part of the consort diagram. The participant must personally sign and date the latest approved version of the informed consent form before any study-specific procedures are performed.

Participants will be given the written and verbal versions of the participant information sheet, interview information sheet and informed consent, which will outline the following: the exact nature of the study;

Clinical Research Protocol Template version 15.0

CONFIDENTIAL

what it will involve for the participant, the implications and limitations of the protocol, the known side effects and any risks associated with participation. The participant will be aware that participation in the study is voluntary, that it is possible to withdraw from the study at any time for any reason, and that no adverse consequences will result from such a withdrawal. In addition, participants will be assured of continuity of care. Their legal rights will remain unaffected, and they will not be obliged to provide a reason for withdrawal. While it is usually a requirement in clinical studies that a participant is offered 24 hours in which to decide whether to take part in a study, given the acute, severe nature of pleural infection and the intervention arm requires a time specific administration of medication to drain the pleural space, a delay of more than a few hours in administering the medication may be detrimental to participant care and delay surgical referral for early surgical assessment and intervention if required. As such, a shortened period of reflection will be offered to participants considering participation in the study, however, investigators will check with potential participants that they understand the study and feel that they have had adequate time to give informed consent. This strategy has been demonstrated to be effective in previous clinical studies of pleural infection. (MIST1, MIST2 and MIST3), (6,11,16) and will be specifically addressed in the ethics application.

Subsequently, the written informed consent of the participant will be obtained utilizing the participant's dated signature and the dated signature of the individual presenting and obtaining the informed consent. The individual responsible for obtaining consent must be suitably qualified and experienced, have been authorised to do so by the Principal Investigator, and have been assigned this responsibility.

The original signed informed consent form will be provided to the participant. A copy will be retained at the study site.

9.4. Baseline assessment

Patients who are willing to participate in the study will have a baseline assessment performed by a member of the research team and documented into relevant CRF. The baseline data will be collected while the participant is in hospital and completed before the patient is discharged. This will include a collection of the following data onto an electronic CRF (REDCap) as follows:

[figure not shown]
- 1. Confirmation of the inclusion and exclusion criteria
- 2. Participant demographics
- 3. Relevant medical history:
 - Co-morbidities (at enrolment) including the presence of chronic renal failure or bleeding disorder
 - Details of the symptoms the participant has had for the current pleural infection (at enrolment) including length of symptoms and nature of the infection (community or hospital acquire infection)
 - Uses of antibiotics before admission to hospital e.g. types and duration
 - Details of the treatment that the participant has had for the current pleural infection (at enrolment i.e. antibiotics, chest drain insertion or therapeutic aspiration)
 - Current medications including antiplatelets and anticoagulants
 - Recent blood test results as part of usual clinical care where available (within 1 week prior to randomization)
- 4. Details of recent radiology results including CXR, and first TUS to be uploaded (videos and images where available) (within 1 week prior to randomization)

5. CT chest will be transferred in a secured USB, Compact Disk or other appropriate password-protected device to Oxford Centre to assess for a radiological pattern of pleural infection e.g., consolidation (within 1 week prior to randomisation)

6. EQ-5D quality of life questionnaire, VAS for chest pain and shortness of breath

9.5. Randomisation

Following consent and baseline assessment, randomisation will occur via a secure web-based system Sealed Envelope by a member of the RAPTOR f research team at the site. Randomisation will occur once the pleural infection has been confirmed by the documented inclusion criteria. This may occur after the therapeutic pleural aspiration or once a chest drain has been inserted or with a high suspicion of pleural infection. Participants will be randomly allocated to one of two arms of the study in a 1:1 ratio to either standard care or RAPID-driven treatment, see study flow diagram (Chart 1). Randomisation will be randomly generated by the Sealed Envelope software to reduce selection bias.

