8.2. Inclusion Criteria

Adults with confirmed pleural infection requiring admission to hospital with ALL of the following:

- 1. A clinical presentation compatible with pleural infection or infective illness
- 2. A pleural collection on radiology (CXR, ultrasound or CT) with a chest drain in situ or planned
- 3. Pleural fluid features diagnostic of infection which is either:
 - A. purulent or
 - B. gram positive or
 - C. culture positive (pleural fluid or biopsy) or
 - D. acidic with a pH<7.2 or
 - E. low pleural fluid glucose <4.4 mmol/L or 72mg/dL(non-diabetic) or LDH ≥ 900 iu/L **OR**
 - F. (non-fluid criteria) CT findings suggestive of pleural infection (pleural enhancement) or pleural fluid septations on thoracic ultrasound
- 4. Willing and able to give written informed consent

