Participants may choose to stop treatment and/or study assessments but may remain on study follow-up, participants may also withdraw their consent, meaning that they wish to withdraw from the study completely. They have the right to withdraw from the study at any time without having to give a reason and this will not affect their future care.

Withdrawal of a participant from the study should be under the guidance of the principal investigator (in liaison with the CI). Withdrawal details will be recorded on the relevant CRF.

Participants are only withdrawn if they specifically request no further data collection. In the event of participants not wishing to attend visits, or to discontinue treatment, they are not considered withdrawn, but this will be recorded as a file note/protocol deviation. Should a participant decide to withdraw, all efforts will be made to complete and report the observations as thoroughly as possible. For participants moving from the area, every effort should be made for the participant to be followed up at another centre, or for follow-up via GP.

Finally, the Investigator may discontinue a participant from the study arms at any time if the Investigator considers it necessary for any reason including:

- I. Ineligibility (either arising during the study or retrospectively having been overlooked at screening)
- II. Significant protocol deviation
- III. Significant non-compliance with the study requirements

If the participant is withdrawn due to an adverse event directly related to the study, the Investigator will

Clinical Research Protocol Template version 15.0

CONFIDENTIAL

Date and version No: 03/06/2025_ V2.0 arrange for follow-up visits or telephone calls until the adverse event has resolved or stabilised.

11. Definition of End of Study

The end of the study is the point at which all the data have been entered, follow-up completed, queries resolved, data lock complete and research samples analysed or at the discretion of the Study Steering Committee (SSC).

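### Section 9.5 permits randomisation on an undefined high suspicion of infection, against 8.2, 9.3 and its own preceding sentence

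*Protocol*

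**What the plan says.** Four parts of the protocol bear on when a patient may be randomised.

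- **Section 8.2** defines the population: "Adults with confirmed pleural infection requiring admission to hospital with ALL of the following". Criterion 3 can be met by a fluid result or, under 3F, by imaging alone: "CT findings suggestive of pleural infection (pleural enhancement) or pleural fluid septations on thoracic ultrasound".
- **Section 9.3** separates consent from randomisation. On consent: "Consent can be obtained prior to confirmation of pleural infection in participants who are likely to have a chest drain insertion". On randomisation of the same people: "These participants will be randomised once the eligibility criteria have been confirmed". It adds: "If pleural infection is ruled out, participants will not be required to continue in the study".
- **Section 9.5** begins with the same rule: "Randomisation will occur once the pleural infection has been confirmed by the documented inclusion criteria". The following sentence says when this may happen: after therapeutic aspiration, once a drain is in, "or with a high suspicion of pleural infection".
- **Section 10** allows the investigator to discontinue a participant from the study arms for several reasons. One is "Ineligibility (either arising during the study or retrospectively having been overlooked at screening".

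Section 13.1.1 defines the recruitment proportion as randomised patients divided by eligible patients, and analyses everyone randomised in the allocated group. The progression table in 13.1.2 sets green at above 50% for the recruitment proportion, and at 90% or more for both adherence and protocol completion.

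**The concern.** The rule for entering the trial should read the same wherever it appears. Here two consecutive sentences of 9.5 disagree. The second offers a route that 8.2 and 9.3 do not have, and its threshold is left to each site in an open-label study at three to four centres.

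The recruitment proportion is one of the main outputs of this feasibility study. It is interpretable only if those counted as randomised are a subset of those counted as eligible. A patient randomised on suspicion who never meets 8.2 breaks that link. The same patient stays in the intention-to-treat comparison without having the disease under study. If discontinued for ineligibility, that patient could also count as a failure of adherence or completion, for a reason unrelated to whether the treatment pathway can be delivered.

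**Working it through.** **1. Does the wording contradict itself?** The word opening the second sentence of 9.5 can refer to randomisation or to confirmation.

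- If it refers to randomisation, suspicion is a way in without confirmation. This conflicts with 8.2, 9.3 and the preceding sentence.
- If it refers to confirmation, suspicion counts as confirmation. This conflicts with 8.2, which requires listed findings.

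Criterion 3F does not resolve this. A patient with CT enhancement or ultrasound septations meets a documented criterion and is already covered by the first sentence of 9.5. The added phrase has work to do only for patients who do not yet meet any item of 8.2(3).

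**2. Effect on the recruitment proportion.** Let E be the number eligible under 8.2, and let u of the 30 randomised never meet 8.2.

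- Reported: 30/E. Among eligible patients: (30 − u)/E. Overstatement: u/E.
- The reported figure is green when 30/E > 0.5, that is E < 60. The figure among eligible patients is not green when (30 − u)/E ≤ 0.5, that is E ≥ 60 − 2u.
- So the colour changes when E is 58 or 59 for u = 1, and when E is 54 to 59 for u = 3.
- Example, with E = 57 and u = 3 both assumed: 30/57 = 52.6% (green) against 27/57 = 47.4% (amber).
- If sites log the three as eligible as well, the figure is 30/60 = 50.0%, which is amber. The result therefore depends on a counting rule that the protocol does not give.

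**3. Effect on adherence and completion.** Inputs: N = 30 (8.1), green at 90% or more, and 10% expected attrition (both from the progression table).

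- 0.90 × 30 = 27. Three losses give 27/30 = 90.0% (green). Four give 26/30 = 86.7% (amber).
- For completion, let q be the share of randomised patients later found not infected. The protocol gives no value, so 0 to 20% is assumed. Assume also that none of them completes, which is the unfavourable extreme. The loss probability is then t = 1 − (1 − q) × 0.90, and the chance of missing green is P(X ≥ 4) with X binomial(30, t).

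| q (assumed) | Expected number, 30q | t | P(4 or more lost) |
|---|---|---|---|
| 0 | 0 | 0.100 | 0.35 |
| 5% | 1.5 | 0.145 | 0.65 |
| 10% | 3.0 | 0.190 | 0.85 |
| 20% | 6.0 | 0.280 | 0.98 |

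**4. Dilution.** The feasibility study is not powered, so the plan's own figure for the definitive trial serves as the yardstick. With a 4-day difference, SD 10, two-sided 5% and 90% power, n per arm = 2 × (1.960 + 1.282)² × 10²/4² = 131.3, rounded up to 132. The total is 264, as section 13.2 states. If the same wording were carried forward, with q = 10% (assumed) and no effect in uninfected patients (assumed), the difference would be 4 × 0.90 = 3.6 days. Power at 264 would fall from 0.90 to 0.83. The stated 30 and 264 do not themselves change.

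**The case against.** The strongest reply is that the phrase does little in practice. Baseline assessment, which includes confirming the inclusion and exclusion criteria (9.4), comes before randomisation. Section 9.12.2 expects a diagnostic aspiration before or at enrolment. Criterion 3F already admits findings that are only suggestive. The sentence might therefore be read as describing timing among patients who already qualify. This is a fair reason to expect few such patients, but the phrase is neither defined nor tied to 3F, so the contradiction stands.

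Several stronger readings are tempting, and the protocol does not support them.

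- *A reader might infer that 9.3 removes these patients after randomisation.* In context, its sentence on infection being ruled out concerns people consented before confirmation and not yet randomised.
- *A reader might infer that the intention-to-treat set is broken.* Section 13.1.1 keeps everyone randomised, and section 10 treats as withdrawn only those who ask for no further data collection. Discontinuation from an arm is not removal from the analysis.
- *A reader might infer that two losses in one arm (13/15 = 86.7%) miss green.* The table sets no per-arm threshold. Two losses give 28/30 = 93.3%, still green.
- *A reader might infer that the RAPID tier cannot be calculated before fluid is seen.* Purulence carries 0 or 1 point. With the boundary between 2 and 3, the tier is open only when the other four items total exactly 2.
- *A reader might infer that losses would differ by arm.* Nothing in the protocol shows that infection would be ruled out more often in one arm.

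**Conclusion.** The contradiction is established from the text alone: 9.5 disagrees with itself, with 8.2 and with 9.3. Followed as written, it can admit randomised patients who never meet the inclusion criteria. The supported consequences are an inflated recruitment proportion, dilution of both arms under intention to treat, and possible discontinuations for ineligibility that count against overall adherence and completion.

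The size is unknown, because the protocol gives no rate for such patients. The recruitment colour changes only when the count lies close to the 50% cut. Completion misses green only at four or more losses from all causes. The probabilities above rest on an assumed q and on the assumption that none of these patients completes. If they are followed to the end, the harm is dilution rather than loss. The point is worth correcting because the wording affects a progression criterion and the correction is small.

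**What to change.** Delete the high-suspicion phrase from 9.5, or replace it with a requirement that an item of 8.2(3), including 3F, is recorded before randomisation. Consent may then precede confirmation, as 9.3 says, but randomisation may not. No further condition, such as known fluid appearance, is needed; it would add to 8.2 and narrow 3F.

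Add one sentence: any randomised patient later found not infected stays in the intention-to-treat set, as 13.1.1 already provides, and is shown separately in the CONSORT diagram. The recruitment proportion can then be read with and without them.

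The cost is one phrase and one sentence. A few patients may be randomised slightly later. Section 9.3 warns against delay of more than a few hours in giving medication, so this is a real trade-off. It should be small, because 3F remains available and the diagnostic aspiration is expected by enrolment. The sample sizes do not change.

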9.6. Blinding and code-breaking

There is no blinding in this study, hence no un-blinding procedures or code-breaking are required.

9.7. Description of study intervention(s), comparators and study procedures (post-randomisation and inpatient period)

Intervention arm

In the intervention arm, treatment will be determined according to the calculated baseline RAPID score.

Patients with a higher RAPID score (and thus higher predicted mortality and morbidity (7,12)) will be triaged to more aggressive treatment early in the disease, and those with lower predicted mortality and morbidity will be treated less aggressively.

A. Low risk (RAPID score 0 to 2):

Patients will be treated as follows:

- 1. Pleural drainage: therapeutic pleural aspiration (drain to dryness) using a Rocket kit will be suggested as the initial treatment. If the patient has already had a chest tube inserted prior to randomisation (as randomisation can occur for 24 hours after drain insertion), then patients will be admitted for drainage for a proposed maximum of 24 to 48 hours, with the removal of the drain as soon as possible, provided there is no residual collection of pleural fluid on the chest-xray (CXR) or thoracic ultrasound or CT scan before drain removal. No specific size of drain is specified, and local practice should be followed.
- 2. **Broad spectrum antibiotics**: see below for the expected standard of care in both intervention groups concerning antibiotics, which are as per NHS standard care for pleural infection. Use of early oral antibiotics to promote discharge is recommended in this group.
- 3. **Review at 3 days +_ 2 days post-discharge** with bloods including full blood count, CRP (Creactive protein), liver and renal profile, ultrasound scan and chest x ray.
- 4. **Patient contact:** All patients will receive a 24-hour contact number (to the study fellow) who can be contacted should there be any concern or deterioration when at home which will prompt urgent review by the pleural service locally.

If at any point a patient is considered to have *failed treatment* on the basis of predefined criteria (see below), they will then be treated as per the intermediate/high-risk group below and will be admitted to hospital.

B. Intermediate + high-risk (RAPID score 3 to 7)

The intermediate and high-risk groups have been combined for the treatment algorithm; there are similar numbers of patients in the combined intermediate and high risk group and the low-risk group (7). Patients in this category will be treated as follows:

- 1. **Pleural drainage:** all patients will be admitted to hospital for chest drain insertion and remain in hospital for as long as is clinically required while the tube is in situ. No specific size of drain is specified, and local practice should be followed.
- 2. Broad spectrum antibiotics: see below; IV antibiotics can be given while the patient is admitted.
- 3. Adjunctive therapy:
 - a. Intrapleural enzyme therapy (tPA / DNase) should be started as soon as possible after drain insertion and randomisation, assuming there are no contraindications. if there is no risk of bleeding.

b. In parallel, referral to local thoracic surgical services made at the time of randomisation, and the need for surgery clinically revisited at 48 hours post-randomisation.

c. In patients where there are contraindications to intrapleural enzyme therapy, immediate surgical intervention in suitable patients should be considered.

Standard care arm:

In the standard care group, the RAPID score *will not be routinely calculated*, and all patients will undergo treatment as per current national guidelines (BTS 2023) (1). This is summarized as follows:

- 1. **Pleural drainage:** all patients will be admitted to the hospital for chest drain insertion and subsequent drainage
- 2. Broad spectrum antibiotics: see below
- 3. **Clinical review** of progression will occur 48 to 72 hours after randomisation and initial above treatment. If there is evidence of poor clinical response (on the objective criteria listed below), the patient will be escalated to either intrapleural therapy or surgical intervention according to patient suitability and clinician choice / usual practice.

Treatment applicable to both arms

A number of treatments should be considered best practice and routine management in patients with pleural infection and will be applied to both groups (intervention and standard care). These treatments follow the NHS standard of care for pleural infection and are as follows:

- 1. **Broad spectrum antibiotics** to cover both aerobic and anaerobic organisms, and according to infection setting (community or hospital acquired infection), to be focused once culture results are available if positive as per local treatment guidelines or policies.
- 2. Intravenous antibiotics should be given during initial admission (if admitted)
- 3. **Switch to oral antibiotics** should occur once there has been a good clinical response with biochemical and radiological improvement, OR if the patient is intended for outpatient treatment (e.g. low RAPID group).
- 4. **Prophylactic low molecular weight heparin** should be administered as per local protocols if the patient is admitted.
- 5. **Analgesics** including NSAIDS or paracetamol in conjunction with opioids if needed will be provided for pain relief from pleural procedures and chest drains.
- 6. **Nutritional support** (supplements, dietician referral, nasogastric feeding) should be considered as clinically appropriate.
- 7. **Chest drain management**; for all patients who have chest drain during treatment, flushes and thoracic suction should be used according to local practice.
- 8. **Clinical review** should be conducted every day by the treating physician.

Treatment failure Criteria

During treatment and follow-up, the following objective criteria will be used to record if the patient is failing treatment and requires further intense treatment including re-admission, intrapleural enzyme therapy or surgical intervention. These criteria apply to any patient at any point from randomization to four weeks follow-up, and regardless of which treatment arm they have been randomised to (and applied in general around 72 hours post randomisation for standard care and medium-high RAPID score in the intervention arm and at day 3 +_ 2 days post-discharge for low RAPID score group or at any other time if the treating physician feels they failed medical therapy). This measure is in place to ensure patient safety and objectivity of decision-making.

The treatment failure criteria are **BOTH** of the following:

- 1. The presence of a **significant residual pleural collection** on radiology (chest radiograph, ultrasound and/or CT) as judged by the local investigator AND
- 2. **At least one** of the following criteria (more than one may apply):
 - a. Clinical evidence of **ongoing sepsis** with persistent fever, tachycardia or hypotension.
 - b. A **serum CRP** (C-reactive protein) that fails to fall by more than or equal to 50% compared to the baseline value (from 48 hours after treatment).
 - c. Lack of significant response in the **peripheral blood white-cell count value** (from 48 hours after treatment) as judged by local investigators.

To ensure objective decision-making and patient safety we will suggest applying **objective discharge criteria** for both arms as the total length of hospital stay is a potentially important primary outcome in the large-scale trial is prove this approach is safe. Discharge will occur **only once all** of the following are met:

- a. Chest drain removed.
- b. No clinical features of sepsis syndrome.
- c. Significantly reduced inflammatory markers according to local physician review.
- d. Significant reduction in pleural fluid on radiology according to local physician review.
- e. Switched to oral antibiotics (at local physician's discretion).

